3.3.1 Risk Assessment

Table 3.3.1-1: Risk Assessment

Potential Risk of Clinical Significance	Summary of Data/Rationale for Risk	Mitigation Strategy		
Study Intervention(s)				
Nonclinical Risk BMS-986196- induced pancreatic toxicity	Pancreatic toxicity of BTK inhibitors is considered rat-specific, (IB Section 7.1.1 and Erickson, et al, 2017 ¹³).	Dose and frequency of administration in Parts A and B is not considered to result in pharmacologically or biologically relevant activity. Testing amylase, lipase, glucose in laboratory panel. Excluding participants with history of pancreatitis (Parts A, B, and C).		
Nonclinical Risk BMS-986196- induced immune suppression	No evidence of infection in non- clinical studies, but BTKi MoA is consistent with immune suppression. (IB Section 7.1.2).	Dose and frequency of administration in Parts A and B is not considered to result in immune suppression or to have pharmacologically or biologically relevant activity. Exclusion of participants with recent or recurrent infections (Parts A, B, andC).		
Nonclinical Risk ¹¹ C-BMS-986196-induced liver injury	In GLP 1-month toxicology study, no liver injury in monkeys and rats. Combined preclinical in vivo and in vitro assessment suggest low risk for liver injury (IB Section 7.1.3).	Dose and frequency of administration in this study is not considered to result in pharmacologically or biologically relevant activity in Part A and B. Exclusion of participants with active hepatitis, ALT or AST > 1.5-fold ULN, total bilirubin > 2-fold ULN (unless in the context of Gilbert Syndrome) (Parts A, B, and C).		
Risk associated with BMS-986196 CNS penetrance/suicidal ideation and behavior (Part C)	IB Section 7.1.1.4	Exclusion of participants who answer "yes" to item 4 or 5 or who answer "yes" to any suicidal behavior item of the C-SSRS (excluding non-suicidal self-injurious behavior) at screening or Day -1. Suicidality will be assessed by the C-SSRS during the study in Part C. Physical examination, including neurological examination, will be performed at screening and during the study.		
Nonclinical Risk associated with BMS-986196 for developmental toxicity (Part C)	IB Section 7.1.1.2	Exclusion of WOCBP from Part C, contraception requirements for male participants.		

Protocol Amendment No.: 05

Table 3.3.1-1: Risk Assessment

Potential Risk of Clinical Significance	Summary of Data/Rationale for Risk	Mitigation Strategy	
Clinical risks associated with therapeutic doses of approved BTKi, including infection, bleeding, arrhythmia, cytopenia, tumor lysis syndrome, secondary malignancy, embryofetal toxicity	Acalabrutinib and Ibrutinib US prescribing information	At the dose and frequency of administration used in the study population, the pharmacological risks associated with BMS-986196 and BTK inhibition are not considered relevant.	
¹¹ C-BMS-986196-associated radiation exposure	CFR, Title 21, Part 361.1(b)(3)(i) Publication 62 of the annals of the ICRP 22 (3), 1992	Risk mitigation by limiting estimated effective dose to < 6 mSv (0.6 rem), below the relevant 10 mSv (1 rem) limit in the UK, based on ICRP standard and below the US-applicable annual effective dose limit of 5 rem (50 mSv), below which radiation exposure car be considered generally safe according to the CFR.	
Study Procedures			
Arterial line placement	Major complications associated with arterial line placement occur in less than 1% of procedures; permanent ischemic damage and pseudoaneurysm occur in 0.09% of procedures 16	Allen's test performed before arterial line placement. Blood coagulation tested at Screening. Arterial line placement performed by experienced staff. Examination of hand/finger circulation after arterial line placement and before discharge. Examination of pressure dressing prior to discharge. Provision of 24 hr emergency phone number. Exclusion of fish oil, aspirin, platelet aggregation inhibitors (including nonsteroidal anti-inflammatory drugs with such activity) and anticoagulants for at least 10 days prior to arterial line insertion and at least 7 days following arterial line removal. (Parts A and B)	
MRI and administration of gadolinium-based contrast agent	Body heat sensation, noise, claustrophobia. Magnetic particles inside the MRI may become projectiles. Electric devices inside the MRI may be damaged. Magnetic implants or particles inside the body may move and/or generate heat. Allergic reactions to gadolinium-based contrast agents. 17	Exclusion of individuals with estimated creatinine clearance < 30 mL/min. Providing adequate ear protection, excluding participants with contraindications to MRI (including non-MRI compatible metal implants/particles, pacemakers, cochlear implants, ventricular shunts, large tattoos in the area affected by the MRI, severe claustrophobia), removing magnetic	

Table 3.3.1-1: Risk Assessment

Potential Risk of Clinical Significance	Summary of Data/Rationale for Risk	Mitigation Strategy	
		objects prior to entering the MRI scanner, excluding participants with known allergy to gadolinium-based contrast agent.	
Other (if applicable)			
SARS-CoV-2 infection risk	During SARS-CoV-2 pandemic, study visits and procedures may increase the risk for infection relative to more socially distanced behavior.	Site-mandated measures for minimization of SARS-CoV-2 transmission. Exclusion of participants with known active SARS-CoV-2 infection.	

Abbreviations: ALT, alanine aminotransferase; AST, aspartate aminotransferase; BTK, Bruton's tyrosine kinase; BTKi, Bruton's tyrosine kinase inhibitor; CFR, Code of Federal Regulations; CNS, central nervous system; C-SSRS, Columbia-Suicide Severity Rating Scale; GLP, Good Laboratory Practices; hr, hour; IB, Investigator's Brochure; ICRP, International Commission on Radiological Protection; MoA, mechanism of action; MRI, magnet resonance imaging; mSv, millisievert; SARS-CoV-2, severe acute respiratory syndrome coronavirus 2; UK, United Kingdom; ULN, upper limit of normal; US, United States.

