2 SCHEDULE OF ACTIVITIES

Study assessments and procedures are presented for screening in Table 2-1 and are presented for imaging assessments and procedures in Table 2-2 (Part A), Table 2-3 (Part B), and Table 2-4 (Part C).

Protocol Amendment No.: 05

Table 2-1: Screening Procedural Outline for Parts A, B, and C (IM038010)

Procedure	Screening Visit(s) (Day -30 to Day -1)	Notes
Eligibility Assessments and Related Procedures		
Informed Consent	X	A participant is considered enrolled only when a protocol-specific informed consent is signed. Must be obtained prior to performing any screening procedures.
Inclusion/Exclusion Criteria	X	
Demographics	X	
Medical History	X	Include any toxicities or allergies related to previous treatments. For Part B, all medical history relevant to MS should be obtained.
Safety Assessments		
Height, Weight, and BMI	X	BMI will be calculated.
Complete PE	X	If the Screening PE is performed within 24 hrs prior to tracer administration on Day 1, then a single complete PE is sufficient for both the Screening and Day 1 PE. See Section 9.4.1.
12-Lead ECG	X	ECGs should be recorded after the participant has been supine for at least 5 min. If the Screening ECG is performed within 24 hrs prior to tracer administration on Day 1, then a single ECG is sufficient for both the Screening and Day 1 ECG. See Section 9.4.5.
Vital Signs	X	VS (including body temperature, respiration rate, seated BP, and HR) should be measured after the participant has been resting quietly in a supine position for at least 5 min. See Section 9.4.3.
Allen's Test	X	Parts A and B only. Normal result must be documented in at least 1 arm.
C-SSRS	X	Part C only. Screening/baseline version with lifetime and 6 months review interval.
SAE Assessment	X	All SAEs must be collected from the time of signing the consent until 10 days after the last tracer administration or the final visit, whichever is later.

Table 2-1: Screening Procedural Outline for Parts A, B, and C (IM038010)

Procedure	Screening Visit(s) (Day -30 to Day -1)	Notes
		All AEs (SAEs and non-serious AEs) associated with SARS-CoV-2 infection must be collected from the date of participant's written consent. See Section 9.2.1.
Prior and Concomitant Medication Use	X	Includes prescription, over-the-counter medications, and herbal supplements. See Section 7.7.1 for Prohibited and/or Restricted Treatments.
Laboratory Tests		

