Procedure	Visit 1 Day 1 ^a	Visit 2 (2 hrs to 6 days after Visit 1 tracer administration)	Safety Follow-up 3 days (± 1 day) after most recent PET Scan ^c /Early Termination ^d	Notes
Safety Assessments				
Weight Measurement	X	X		
Partial PE	X	X		PE must be done within 24 hrs of tracer administration. Symptom-based PE only.
12-Lead ECG	X	X		ECGs should be recorded after the participant has been supine for at least 5 min. ECG will be conducted prior to tracer administration and after completion of the PET scan. See Section 9.4.5.
Vital Signs	X	X		VS will be obtained before tracer administration, after PET scan completion, and prior to discharge on Visits 1 and 2. See Section 9.4.3.
Allen's Test		X		Normal result (in the arm that will be used for arterial line placement) must be documented prior to arterial line placement.
Hematology, Chemistry, Urinalysis	X	X		Participants are required to fast for at least 10 hrs prior to specimen collection. Specimens will be collected at least 1.5 hrs after the first tracer administration and at least 1.5 hours after the second tracer administration. See Section 9.4.6 for full list of clinical laboratory safety tests/assessments.
Pregnancy Test (WOCBP only)	X	X		Urine or serum test. Result must be confirmed as negative prior to tracer administration on Day 1.
Review of Emergency Contact Instructions	X	X		Prior to discharge on Visits 1 and 2.

Table 2-2: Imaging Procedural Outline for Part A (IM038010)

Procedure	Visit 1 Day 1 ^a	Visit 2 (2 hrs to 6 days after Visit 1 tracer administration) ^b	Safety Follow-up 3 days (± 1 day) after most recent PET Scan ^c /Early Termination ^d	Notes
Non-serious AE and SAE Assessments	X	X	X	All SAEs must be collected from the time of signing the consent until 10 days after the last tracer administration or the final visit, whichever is later. All AEs (SAEs and non-serious AEs) associated with SARS-CoV-2 infection must be collected from the date of participant's written consent. See Section 9.2.1.
Concomitant Medication Use	X	X	X	
Imaging Assessments and Subseq	uent Procedures			
Arterial Line Placement		X		Prior to tracer administration.
Venous Line Placement for Venous Blood Sampling (During Visit 2 PET Scan)		X		Prior to tracer administration (on the arm opposite to the tracer administration). Only in up to 2 participants (added to Part A after initiation of Part B) undergoing simultaneous arterial and venous blood sampling.

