^a Visit 2 tracer administration must be done at least 2 hours after and at most 6 days after Visit 1 tracer administration. If Visit 2 is performed on Days 5, 6, or 7, the site staff must contact the participant remotely (ie, by phone) on Day 4 and record AEs and concomitant medications. Participants who had a within 30 days prior to Day 1 must start Scan 2 on Day 1 or Day 2. If 2 scans are performed on the same day, VS measurement, ECG, and review of AEs and concomitant medications are the only safety assessments that must be assessed in duplicate, and the same arterial line may be used for both scans.

b If the interval between Visit 1 (PET Scan 1) and Visit 2 (PET Scan 2) is ≥ 4 days, 2 follow up remote contacts (ie, phone calls) must be performed. In this case, each follow up contact will be performed 3 days (± 1 day) after the most recent PET scan.

^c For participants who are prematurely discontinued from the study.

d Dynamic PET image acquisition.

^e A third administration is permissible if a PET scan has to be repeated (eg., due to failure of a prior scan).

Table 2-4: Imaging Procedural Outline for Part C (IM038010)

Procedure	Visit 1 Day 1	Visit 2 approximately 24 hrs after the last dose of BMS-986196 (Days 2-9)	Visit 3 7 Days (±2) after Visit 2/ET	Visit 4 (28 - 31 days after Visit 3)	Notes
In-person Visit to Clinical Site	X	X	X		
Phone call/Telemedicine visit				X	In-person visit is optional. Email or text messaging is not sufficient.
Safety Assessments					
Weight Measurement			X		
Partial PE	X	X	X		
12-lead ECG	X	X	X		
Vital Signs	X	X	X		
Hematology, Clinical Chemistry, Urine analysis	X		X		Participants are required to fast for at least 10 hrs prior to specimen collection. Specimens will be collected prior to tracer administration on Visits 1 and 2. See Section 9.4.6 for full list of clinical laboratory safety tests/assessments.
C-SSRS	X	X	X		Since last visit version of C-SSRS.
Review Emergency Contact Information	X	X	X		
AE and SAE assessment	X	X	X	X	All AEs and SAEs must be collected from the time of signing the informed consent form, including those thought to be associated with protocol-specified procedures and until 28 days following discontinuation of dosing.
Concomitant Medication Use	X	X	X	X	
Imaging Assessments and	d Procedu	ires			
Venous Line Placement for Blood Sampling	X	X			Prior to tracer administration (on the arm opposite to the tracer administration).

32

Table 2-4: Imaging Procedural Outline for Part C (IM038010)

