In this study, 11 C-BMS-986196 will be dosed at microdoses of up to 20 µg, which is below the general microdose criterion of 100 µg for small molecule PET ligands. At doses of up to 20 µg, 11 C-BMS-986196 is not expected to elicit meaningful biological or pharmacological effects. Concurrent with this study, Study IM038008 is testing the safety, tolerability, pharmacokinetics, and target engagement as pharmacodynamics of BMS-986196 in healthy participants. In Study IM038008, the starting dose of unlabeled, orally administered BMS-986196 is 1 mg, which is projected to not have biologically meaningful effects and result in area under the plasma concentration-time curve (AUC) exposure more than 1,000-fold below that at the no-observed-adverse-effect level (NOAEL) from the 1-month toxicology studies. The AUC exposure associated with single intravenous (IV) administration of 20 µg 11 C-BMS-986196 is projected to be approximately 7.5-fold below the exposure associated with an oral dose of 1 mg. Orally administered doses \geq 10 mg are projected to result in peak BTK occupancy > 95% in blood, and therefore, are projected to approach therapeutic levels.

In Part C of this study, non-radioactively labeled (unlabeled) BMS-986196 will be administered at dose levels up to 60 mg once daily (QD) up to 7 days. Hence, in Part C, (unlabeled) BMS-986196 will be administered at therapeutic dose levels and is expected to result in near maximum BTK occupancy. In Study IM038008, the first-in-human study testing unlabeled BMS-986196 at therapeutically relevant doses, administration of BMS-986196 at doses up to 90 mg QD for 14 days was shown to be safe and tolerated.

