9.4.1 Physical Examinations

A complete PE includes examination of head, eyes, ears, nose, and throat (HEENT), heart, lungs, abdomen, extremities, skin and in Parts A and C only, a limited neurological exam. In Part B, the serves as neurological examination. A partial PE will be symptom-oriented and include areas with previously noted abnormalities and/or newly emergent symptoms.

Complete and/or partial PEs may be performed by a Doctor of Medicine, or someone who is authorized to perform the examinations by training and has been delegated this task by the investigator. Every effort should be made to ensure the same evaluator will complete the examination for each participant at all visits throughout the study. Documentation of the person who performed the examination is to be recorded in source notes.

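### Part C: the risk table lists a neurological examination during the study as mitigation for CNS risk, but none is required after unlabeled BMS-986196 is given

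*Protocol*

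**What the plan says.** Table 3.3.1-1 of the protocol has a row for CNS penetrance and suicidal ideation or behavior with BMS-986196, marked as a Part C risk. Besides exclusion and monitoring by C-SSRS, it lists: "Physical examination, including neurological examination, will be performed at screening and during the study".

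Section 9.4.1 defines two kinds of PE. The complete PE covers the body systems and adds, "in Parts A and C only, a limited neurological exam". The other kind is narrower: "A partial PE will be symptom-oriented and include areas with previously noted abnormalities and/or newly emergent symptoms". The Part A schedule (Table 2-2) uses the term in the same way; its note on the partial PE reads "Symptom-based PE only".

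Table 2-1 schedules the complete PE at Screening. It allows that PE to serve for Day 1 as well: "If the Screening PE is performed within 24 hrs prior to tracer administration on Day 1, then a single complete PE is sufficient". Table 2-4, the Part C schedule, has a Partial PE row marked at Visits 1, 2 and 3. It shows no complete PE row and no neurological exam row. Visit 4 is a remote contact by default, with no PE. Unlabeled BMS-986196 starts after the Visit 1 PET procedure or on Day 2. The two later in-person visits are headed "Visit 2 approximately 24 hrs after the last dose of BMS-986196 (Days 2-9)" and "Visit 3 7 Days (±2) after Visit 2/ET".

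**The concern.** The risk in this row comes from therapeutic doses of unlabeled drug. An examination done before the first dose gives a baseline but cannot detect an effect of the drug. An ethics committee or site reading the risk table would expect a neurological exam to be part of Part C follow-up. A site following Table 2-4 and Section 9.4.1 has no instruction to do one in a participant without complaints, and Section 9 makes adherence to the Schedule of Activities mandatory.

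At stake is one narrow safeguard: finding a neurological sign that the participant has not noticed or mentioned. It is relevant because the safety of BMS-986196 is a primary objective and clinically significant PE abnormalities belong to a primary endpoint (Table 4-1). Section 9.4.7 also describes the drug as CNS-penetrant, with unknown effects on mood and suicidality.

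**Working it through.** The plan states no figure here, so the check sets the text against the schedule.

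**Step 1: where a neurological exam is mandatory in Part C.**

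| Occasion | PE scheduled | Relation to unlabeled drug | Neurological exam required? |
|---|---|---|---|
| Screening (Table 2-1) | Complete | Before | Yes |
| Visit 1, Day 1 (Table 2-4) | Partial; the Table 2-1 note can be read as implying a complete one | Before | Only if read as complete |
| Visit 2 (Table 2-4) | Partial | After | Only if prompted |
| Visit 3 (Table 2-4) | Partial | After | Only if prompted |
| Visit 4 (Table 2-4) | None | After | No |

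Table 2-4 gives no clock time for the Visit 1 PE. I place it before dosing because the Table 2-1 note ties the Day 1 PE to the time before tracer, and unlabeled drug follows the PET procedure.

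**Step 2: the count.** With the planned maximum of 12 evaluable participants:

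- PEs in Table 2-4: 3 visits × 12 = 36, all labeled partial.
- PEs after unlabeled dosing: 2 visits × 12 = 24.
- Of those 24, PEs requiring a neurological exam: 0 as written; 24 with the fix below.

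This counts scheduled examinations. It does not estimate harm.

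**Step 3: what exams at Visits 2 and 3 could show.** Visit 2 is about 1 day after the last dose. Visit 3 is 7 ± 2 days after Visit 2, so it falls 1 + 5 = 6 to 1 + 9 = 10 days after the last dose.

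For plasma drug at Visit 2, Section 3.2.7 reports a terminal half-life of about 3 to 5 h after repeat dosing, and Section 3.3 projects about 6 h for the tracer form of the molecule. With simple exponential decline, the fraction left at 24 h is 2^(−24/half-life):

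- 3 h: 2^(−24/3) = 2^(−8) = 0.4%
- 5 h: 2^(−24/5) = 2^(−4.8) = 3.6%
- 6 h: 2^(−24/6) = 2^(−4) = 6.25%

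So roughly 0.4% to 6% remains, assuming that the tablet taken with food behaves similarly. This is a range under an assumption, not a bound: slower absorption would leave more. An exam at Visit 2 would therefore look for signs that persist, not for effects confined to peak levels.

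**The case against.** The strongest reply is that the risk table promises an exam during the study and does not say after dosing. The Table 2-1 note suggests that the Day 1 PE is complete unless the Screening PE replaces it, so a Day 1 exam could meet the words literally. That stands as a reading of the words. It requires treating the Visit 1 PE as complete although Table 2-4 labels it partial, and the exam would still precede the drug whose risk the row addresses.

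Second, the partial PE does reach the nervous system when there are symptoms or earlier abnormalities. C-SSRS and adverse event assessment are scheduled at Visits 2 and 3. Section 9.4.7 asks for close observation for suicidality and unusual changes in behavior. All of this stands. It limits the gap to unreported signs, but the table commits to the exam in addition to C-SSRS and without conditions.

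Third, the published schedule may be incomplete. Section 9.4.1 has a gap where the Part B neurological assessment is named, so a neurological row could have been removed elsewhere. Table 2-4 shows no sign of a missing safety row, but this cannot be ruled out.

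A reader might also infer that continuing BTK occupancy at Visits 2 and 3 makes silent neurological effects likely. The documents do not support that. The Introduction says that Part C dosing "is expected to result in near maximum BTK occupancy", but the projection of 50% recovery within 7 days in Section 9.3 concerns tracer overdose. Section 3.2.7 gives about 50% at 7 days for Part C doses, with the measure blacked out. Neither figure is identified as brain BTK. Section 3.2.1 adds that neurons, astrocytes and oligodendrocytes do not express BTK and that it has no known function in a healthy CNS.

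**Conclusion.** The mismatch is real and minor. On the visible text, the only mandatory neurological exam in Part C precedes unlabeled BMS-986196, and both scheduled PEs after dosing are symptom-oriented. This rests on three readings: the Section 9.4.1 definitions apply to Table 2-4, the Visit 1 PE comes before unlabeled dosing, and no neurological row was removed from that table.

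It would be too strong to say that participants have no CNS monitoring after dosing, or that harm is likely to be missed. Suicidality, behavior change and reported symptoms are covered. The rat neurologic safety pharmacology study showed no CNS effects (Section 3.2.6). In IM038008, at up to 90 mg once daily for 14 days, there were no serious or severe adverse events (Section 3.2.7).

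The practical reach is also limited. SAP Section 6 says that Part C dosing will not continue and that its later sections cover Parts A and B only. No planned analysis changes. The point matters for the Part C protocol text if that part is reopened or its wording reused.

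**What to change.** In Section 9.4.1, add that in Part C the PE at Visits 2 and 3 includes the limited neurological exam already defined there. Put the same note in the Partial PE row of Table 2-4, so that sites see it where they plan visits.

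The cost is a few minutes at two visits that are already in person, with no new procedure or visit. The exam would not capture effects limited to the hours around peak concentration.

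If the sponsor judges the exam unnecessary, rewording Table 3.3.1-1 to describe a symptom-oriented PE after dosing would also remove the mismatch. I prefer adding the exam, because it delivers at little cost a safeguard that the protocol already lists.

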3.3.2 Benefit Assessment

Administration of ¹¹C-BMS-986196 does not confer any therapeutic benefit to study participants. Participating in this study contributes to research and to the development of a compound that can visualize inflammation in the CNS in a novel way and that can help develop therapies for progressive MS. Participants will undergo medical evaluations including a physical examination, ECGs, and clinical laboratory safety tests, and a cranial PET scan.

